8.5. Interim Analysis and Data Monitoring

No formal interim analysis or data monitoring is planned for this study. However, a safety review panel will conduct blinded reviews during Part A and select the doses to be used in Part B.

8.6. Multiple Comparison/Multiplicity

This is a dose-finding study with no formal sample size calculation; thus, no adjustment for multiple comparisons is performed. All statistical comparisons planned for this study are exploratory.

8.7. Examination of Subgroups

Analyses based on subgroups of interest may be carried out for exploratory purposes. Possible analyses include the following:

- Gender: Female, Male.
- Wart Location: Medial Thigh, Supra-Pubic, Perineal, Perianal Area, Glans Penis, Penis Shaft, Scrotum, Foreskin, Vulva
- Wart Location by Gender
- Number of warts at baseline: 2-10, 11-20, 21-30
- Fitzpatrick Skin Type: I or II, III or IV, V or VI
- Duration of warts: <1 yr., 1-2 yrs., >2 to 5years, >5 years.

9. Methods of Efficacy Analysis

9.1. Complete Clearance of Treatable Warts

Counts and percent of subjects who have complete clearance of all treatable warts will be displayed by visit; however, the primary analysis is complete clearance at Study Day 84 EOT. The row mean scores statistic from the Cochran-Mantel-Haenszel (CMH) test will be used to analyze differences in each treatment regimen (VP-102 Regimen 1 vs Placebo Regimen 1 and VP-102 Regimen 2 vs Placebo Regimen 2) by gender. Complete clearance will be defined as no warts (treatable wart count=0) reported for a subject per the blinded EGW Wart Count form. This analysis will be done on the primary endpoint, Study Day 84, as well as each of the other visits.

Also analyzed will be the proportion of subjects who have complete clearance at Day 84 and remained clear through the end of the study, follow-up visit Day 147. The CMH test will be used to test for treatment differences.

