8.7 Previous and Concomitant Medications

All medications taken within 14 days prior to the first dose of the study drug will be classified as prior medication; while all medications used after the first dose of study drug will be classified as concomitant medications. Prior and concomitant medications will be recorded in the eCRF, along with the reasons for administration and durations of use.

Treatment of warts with any prescription or over-the-counter wart medication (including any HPV immunization), curettage, or freezing of warts should not be implemented during the study. Treatments for genital warts include, but are not limited to, the use of cantharidin, antivirals, retinoids, salicylic acid, lactic acid, hydrogen peroxide, candida antigen, diphencyprone, dinitrochlorobenzene, sandalwood oil, thuja oil, squaric acid dibutyl ester, povidone iodine, nitric oxide, any other over-the-counter wart treatment; curettage; or freezing of warts.

Potential subjects who are systemically immunosuppressed or have required, or will require, systemic immunosuppressive or immunomodulatory medication (including oral or parenteral corticosteroids) within 30 days before enrollment or during the course

of the study will be excluded. Note that routine use of local (e.g., topical, inhaled, or intranasal) corticosteroids during the study is allowed.

Immunizations and flu shots may be administered throughout the study but not within 5 days before or after treatment.

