 - If there are no warts remaining, the same areas will be photographed regardless of whether warts are present
- Assess, identify, and record any new AEs
- Record any new concomitant medications
- Complete Provider questionnaire; by a clinician who applied treatment to the subject during the course of the study

9.5 Follow-up Visits on Study Day 112 (± 7 days) and Study Day 147 (± 7 days) (End-of-Study)

Subjects will return to the clinical site and the following evaluations will be performed and recorded in the eCRF.

- Clinical assessments
 - Measure height and weight
 - Measure vital signs (temperature, heart rate)
- Wart assessments
 - Wart count conducted before dermatologic exam and ERT assessments
 - Conducted by a designated Blinded Assessor; Blinded Assessors are trained to the study and GCP, and listed on the FDA FORM 1572 and the site Delegation of Authority Log; the Blinded Assessor does not have to be the same person at each visit

-
- Also conducted by a study team member who is not considered, or has not acted as, the Blinded Assessor for the subject throughout the subject's participation
 - Wart anatomical location identified before dermatologic exam and ERT assessments
 - Conducted by a study team member who is not considered, or has not acted as, the Blinded Assessor for the subject throughout the subject's participation
 - Warts that develop in areas that are unable to be treated, (e.g., close to a mucous membrane) will not be evaluated, documented, or considered in the analysis
 - Wart measurement (diameter and area) conducted before dermatologic exam and ERT assessments
 - Conducted by a study team member who is not considered, or has not acted as, the Blinded Assessor for the subject throughout the subject's participation
 - Dermatologic exam by anatomical location
 - Conducted by a study team member who is not considered, or has not acted as, the Blinded Assessor for the subject throughout the subject's participation
 - Laboratory assessments
 - Perform urine pregnancy test on female subjects of child-bearing potential (i.e., females who are capable of menstruating)
 - ERT assessment
 - Only collect new information since the last contact
 - All ERT safety assessments must be conducted and recorded on ERT by a qualified member of the research team before study drug application; ERT assessments must be conducted by a study team member who is not considered,

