8.4. Handling of Dropouts or Missing Data

All subjects who were randomized will be evaluated in the ITT population. If a subject requests to be removed from the study due to study related adverse events or additional spreading of disease, data will be collected and analyzed as a treatment failure and not replaced. If a subject discontinues use of study drug but remains in the study, the subject will be analyzed as a non-responder as well. Per the study protocol, subjects who achieve complete clearance of all lesions prior to Day 84 are required to attend all Treatment Visits but will not receive treatment at those visits where all lesions are clear. These subjects will not be considered as having prematurely discontinued use of the study drug.

Unless described otherwise in subsequent sections, analyses will be carried out with the data available using no imputation for missing data. A description of how missing data will be handled for select endpoints is included below.

8.4.1. Coronavirus 19

Due to the coronavirus 19 (COVID-19) outbreak during the course of the study, there may be several subjects who will have missing assessments which could affect the primary analysis. Subjects who are unable to attend a study visit due to COVID-19 will be documented in the protocol deviation log. The protocol deviation date will be used as the COVID-19 affected date (or visit). If a subject reports an adverse event of COVID-19, then the event start date will be used as the affected date. In the event that a subject has an affected COVID-19 date from both sources, the earlier of the dates will be used.

Subjects who were affected by COVID-19 will be summarized in a data listing. The listing will contain the following information: subject number, treatment, gender, age, first date affected by COVID-19, duration in study prior to the affected COVID-19 date, total study duration, exposure to study drug, any COVID-19 related adverse events, completion/discontinuation of the study, and reasons for discontinuation. All data listings will include a flag to denote whether the subject and/or visit was affected by COVID-19.

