8.4.2. Handling of Missing Data for Complete Clearance Endpoint

The efficacy endpoint, proportion of subjects exhibiting complete clearance of all treatable warts, is to be assessed (blinded assessment only) at Treatment Visits 2, 3, 4, Study Day 84 EOT visit, and Follow-up visits Day 112 and 147.

For the primary efficacy analysis, subjects who do not have an assessment of complete clearance of all treatable warts at any of the scheduled assessments (with applicable visit windows applied) will be considered to have not achieved complete clearance of all treatable warts at that visit.

Due to COVID-19, sensitivity analyses will be performed to assess the robustness of the primary analysis. The purpose of these analyses is to assess any potential bias due to subject assessments or missing data due to COVID-19. There will be two sensitivity analyses on the primary efficacy endpoint, complete clearance at Day 84.

- Exclude COVID-19 affected data: The first analysis will be to conduct the planned analysis only on the subjects who were not affected by COVID-19 at or before Day 84 (with visit window), i.e., if a subject was affected by COVID-19, then the subject will be removed from the analysis.
- Multiple imputation of missing data: The second analysis will be to use the multiple imputation regression method. For monotone missing data patterns, data in each treatment group will be imputed using the regression method on the basis of the predicted future pattern for the same treatment group. One hundred imputed

datasets will be generated. Each imputed dataset is analyzed separately using the method for the efficacy endpoint described in 9.1. The final estimate of treatment difference will be the average of the estimates based on the 100 individual imputed datasets. The pooling of the individual estimates and inferences based on the combined estimate will be handled by the SAS procedure MIANALYZE.

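### Clearance is credited to any zero wart count whatever its cause, and no ITT rule scores a subject who stays in the study and uses a prohibited non-study wart treatment

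*SAP*

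**What the plan says.** SAP 9.1 defines the endpoint by the count alone: "Complete clearance will be defined as no warts (treatable wart count=0) reported for a subject per the blinded EGW Wart Count form". It applies that definition at every visit: "This analysis will be done on the primary endpoint, Study Day 84, as well as each of the other visits". SAP 8 makes ITT (all randomized subjects) the primary population.

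The documents contain these rules that override or replace the count:

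- SAP 8.4, withdrawal at the subject's request for study-related adverse events or spread of disease: "data will be collected and analyzed as a treatment failure and not replaced".
- SAP 8.4, stopping drug: "If a subject discontinues use of study drug but remains in the study, the subject will be analyzed as a non-responder as well". Subjects who go untreated because they are already clear are exempt: "These subjects will not be considered as having prematurely discontinued use of the study drug".
- SAP 8.4.2, a subject with no assessment at a visit: "will be considered to have not achieved complete clearance of all treatable warts at that visit".
- Protocol 7.6, a subject who does not complete the study is a failure for the primary endpoint.

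Non-study wart treatment is prohibited throughout by Protocol 7.1 (inclusion 8), 7.2 (exclusion 13), 8.7 and 9.1. Section 8.7 names procedures as well as drugs: "curettage, or freezing of warts should not be implemented during the study". None of these sections says how a subject who breaks the rule is analyzed.

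**The concern.** The SAP already treats one post-randomization event, stopping study drug, as non-response whatever the later count. Using a rival wart treatment bears on the meaning of a zero count at least as directly, yet by default it counts as success. A subject who has had all four applications, has the remaining warts frozen around Day 70 and shows a zero count at Day 84 is a responder for the assigned arm.

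Exposure is greater after Day 84. Protocol 6.4 allows no treatment after Day 75 without sponsor approval, so follow-up runs to Day 147 without planned dosing. A subject who turns to another treatment in that period has no study drug left to stop, so the stop-drug rule cannot apply. A recurrence treated elsewhere between visits can still count as sustained clearance.

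These rates matter even without a confirmatory test. Part B is meant to identify the regimen with the best risk:benefit profile (Protocol 5.0), and the clearance rates are meant to inform assumptions for later placebo-controlled trials (Protocol 12.6).

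**Working it through.** The documents give no clearance rate, effect size or power, so there is no planned figure to reproduce. The check traces the scoring rules and then sizes one subject.

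**Step 1. Which rule catches a user of prohibited treatment?**

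| Situation | Rule that applies | Score |
|---|---|---|
| Uses it and asks to be removed because of adverse events or spread | SAP 8.4 | Failure |
| Uses it and stops study drug while warts remain | SAP 8.4 | Non-responder |
| Uses it and has no Day 84 count | SAP 8.4.2 | Not cleared |
| Uses it and does not complete the study | Protocol 7.6 | Failure (primary endpoint) |
| Uses it, stays in, has had all applications, count 0 | None | Responder |
| Uses it between treatment visits, count 0 at the next, so is not treated | SAP 8.4 exemption | Responder |
| Uses it after planned dosing, count 0 at Day 112 or 147 | None | Responder |

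The PP population (SAP 6) drops such a subject only if the deviation is classed as major, and major is not defined. Discontinuation for noncompliance (Protocol 7.4.3) is discretionary.

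**Step 2. Arm sizes per regimen.** Part B has about 90 subjects in the ratio 3:3:2:2 (Protocol 6.1.2): 90 × 3/10 = 27 VP-102 and 90 × 2/10 = 18 placebo per regimen. Each Part A group of six is split 5:1 and pooled if its regimen is selected (SAP 3 and 5). Pooled: 27 + 5 = 32 VP-102 and 18 + 1 = 19 placebo.

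**Step 3. Effect of one subject.** Placebo: 1/19 = 5.3 points. VP-102: 1/32 = 3.1 points.

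**Step 4. Illustration with assumed counts.** For a single stratum (sex ignored), with x1 of n1 VP-102 responders, m responders in total and N subjects, the CMH statistic is Q = (x1 − n1·m/N)² / [n1·n2·m·(N − m) / (N²(N − 1))], referred to chi-square on 1 df.

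| VP-102 | Placebo | Difference (points) | p |
|---|---|---|---|
| 11/32 | 1/19 | 29.1 | 0.019 |
| 11/32 | 2/19 | 23.8 | 0.061 |
| 11/32 | 3/19 | 18.6 | 0.155 |
| 9/32 | 1/19 | 22.9 | 0.049 |
| 8/32 | 1/19 | 19.7 | 0.077 |

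First row in full: N = 51, m = 12, n1·m/N = 7.529, variance = 32 × 19 × 12 × 39 / (51² × 50) = 2.188, Q = (11 − 7.529)² / 2.188 = 5.51. Rows 2 and 3 add one and two placebo subjects cleared by outside treatment. Rows 4 and 5 remove two and three VP-102 responders, as would happen if their clearance came from outside treatment and were rescored.

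**Step 5. Direction at Day 147, all inputs assumed.** Suppose 17 of 19 placebo subjects are uncleared, 10–20% of them use another treatment and half of those clear: 17 × 0.10 × 0.5 = 0.85 to 17 × 0.20 × 0.5 = 1.7 subjects, or 4.5 to 8.9 points on the placebo rate. With the same use among an assumed 20 of 32 uncleared VP-102 subjects, the gain is 1 to 2 subjects, or 3.1 to 6.3 points. The net dilution is then about 1.3 to 2.7 points. Different use by arm could make it larger or reverse it.

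**The case against.** The plan is not blind to such use. Drugs and HPV immunization are asked about at every contact (Protocol Table 1; for example "Record any new concomitant medications" in 9.4), with the reason for use recorded (Protocol 8.7), and medications are tabulated by arm (SAP 10.8). Any departure from the protocol is a deviation (Protocol 12.9), and deviations are collected throughout (SAP 7.2). A reader might infer that outside treatment would go unrecorded; the documents do not support that. What remains is narrower. Wart-treatment history is scheduled only at Screening and Treatment Visit 1, and no later visit lists a specific prompt for procedures such as freezing or curettage. The eCRF itself is not among the documents.

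A reader might also infer that the SAP penalizes VP-102 and rewards placebo. It does not: the stop-drug rule applies equally to both arms and spares subjects who are untreated because they are clear. Nor can treatment received after Day 94 affect the primary endpoint, because the Day 84 window in SAP 8 closes then.

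The fairest objection is that using the observed count whatever other treatment was given is a recognized treatment-policy strategy, and that all comparisons are declared exploratory (SAP 8.6). Both points are true. But the SAP does not state that choice, and it takes the opposite approach for stopping drug. Exploratory status limits the consequence without settling how these subjects are scored.

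**Conclusion.** The gap is real. Followed as written, the primary ITT analysis scores as a responder any subject who stays in the study, is cleared by prohibited treatment and is caught by none of the listed rules. The conclusion rests on the plan's silence combined with the zero-count definition; no sentence expressly calls such users responders.

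The firm size is 5.3 points per placebo subject and 3.1 points per VP-102 subject, at about 19 and 32 per regimen. Under the assumed counts above, a single placebo subject moves p from 0.019 to 0.061.

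A reader might go further and conclude that the gap dilutes the treatment effect because placebo subjects guess their arm and seek treatment elsewhere. That is plausible, but the documents give no usage by arm. The 4.5 to 8.9 points is a gross Day 147 figure that assumes no use on VP-102; similar use in both arms leaves about 1.3 to 2.7. Clearance by outside treatment on VP-102 would inflate the difference instead.

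**What to change.** Add to SAP 8.4, with a cross-reference in 9.1: a subject who receives any non-study treatment given for genital warts (drug, HPV immunization, or a procedure such as freezing or curettage) is a non-responder for complete, 90% and 75% clearance, reduction of at least one wart, and sustained clearance, at every assessment on or after that date.

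The limit to treatment given for genital warts is needed because the list in Protocol 8.7 includes antivirals, hydrogen peroxide and povidone iodine, which may be used for other reasons.

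Identify users from concomitant-medication data (with indication) and protocol-deviation data in a blinded review before database lock. Report the number of users by arm. Keep the observed-count (treatment-policy) result as a sensitivity analysis.

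Whether wart counts after such use should stay in the MMRM is a separate estimand choice and need not be settled here. New eCRF questions should not be relied on: the SAP was written after COVID-19 arose during the study, so visits may already have been held.

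The cost is a short SAP addition, one blinded listing review and one extra run of the clearance analyses. Observed clearance rates may be slightly lower, and procedures not recorded as deviations may be missed.

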9.2. Change and Percent Change in Number of Warts

Number of warts present will be recorded at each treatment visit as well as follow-up visits. For each post baseline treatment visit, the change in number of warts from baseline will be calculated. Summary statistics of number of warts will be displayed for each treatment visit. Summary statistics of change in number of warts from baseline will also be displayed. Statistical analyses on each treatment regimen will be performed. A restricted maximum likelihood-based repeated-measures approach, using a Mixed effect Model Repeat Measurement (MMRM) will be used. The MMRM model will include the fixed, categorical effects of treatment, gender, visit, and treatment-by-visit interaction as well as the continuous, fixed covariate of baseline wart count. An unstructured (co)variance structure shared across treatment groups will be used to model the within-subject errors. If convergence is not met, then the Akaike's Information Criteria will be used to select the best covariance structure to model the data. The Kenward-Roger approximation will be used to estimate denominator degrees of freedom and adjust standard errors.

Percent change of warts will be calculated at each post baseline visit. Percent change will be calculated using the following formula (in formula below, warts refers to treatable warts):

$$\text{Percent (\%) Change} = \frac{(\text{Warts}_{\text{Visit}} - \text{Warts}_{\text{Baseline}}) / \text{Warts}_{\text{Baseline}}}{1} * 100$$

Analysis of percent change in number of warts will be carried out in the same manner as change in number of warts.

An additional analysis will be carried out by visit to report the number and percent of subjects who had a reduction of one or more treatable warts from baseline. The proportion of subjects with 90% and 75% clearance of warts will also be analyzed using a CMH test.

9.3. Reduction of Wart Area

At Visit 1, Study Day 84 EOT, 112, and 147, the total wart area will be measured and reported on the CRF. The change and percent change in wart area will be calculated for each post baseline visit and will be summarized using summary statistics. The percent change will be calculated using the same formula described in Section 9.2 (using wart area rather than number of warts).

10. Safety Analysis

All safety analysis will be based on the Safety Population. Analyses using the Safety population will be based on the treatment received.

10.1. Extent of Exposure

The total number of warts treated will be collected by visit over the duration of the study. For each visit, the number of warts treated will be determined by taking the number of warts reported on the EGW Wart Count at Visit 1 and from the Blinded Assessment of Warts form at subsequent visits. The total number of treatment visits and total number of warts treated will be displayed.

10.2. Adverse Events

Adverse events summaries will only consider Treatment Emergent Adverse Events (TEAEs). TEAEs are defined as those adverse events that occurred after dosing and those existing adverse events that worsened during the study. If it cannot be determined whether the adverse event is treatment emergent due to an incomplete (partial) onset date, the adverse event will be considered treatment emergent. Verbatim terms entered into the clinical database via the EDC system will be mapped to preferred terms and system organ classes using the Medical Dictionary for Regulatory Activities (MedDRA) Version 23.0.

Each adverse event summary will be displayed by treatment group. Summaries that are displayed by system organ class and preferred terms will be ordered by descending order of incidence of system organ class and preferred term within each system organ class. Summaries of the following types will be presented:

- Overall summary of the TEAEs which contain an overview of each item below.
- Subject count and incidence rate of TEAEs by MedDRA system organ class and preferred term.

- Subject count and incidence rate of TEAEs by MedDRA system organ class, preferred term and highest severity. At each level of subject summarization, a subject is classified according to the highest severity if the subject reported one or more events.
- Subject count and incidence rate of TEAEs by MedDRA system organ class, preferred term and closest relationship to study drug (Related/Not Related). Related AEs are those reported as “Definitely”, “Probable” or “Possibly”. At each level of subject summarization, a subject is classified according to the closest relationship to study drug if the subject reported one or more events. Adverse events with missing relationship will be considered related for this summary.
- Subject count and incidence rate of Serious TEAEs by MedDRA system organ class and preferred term.
- Subject count and incidence rate of TEAEs leading to study discontinuation by MedDRA system organ class and preferred term.
- Subject count and incidence rate of TEAEs by MedDRA system organ class and preferred term by gender

In addition to the above, TEAEs by system organ class and preferred term will be summarized on events that occurred prior to a subject’s COVID-19 affected date and also for events that occurred after a subject’s COVID-19 affected date.

